4.0 Statistical Analysis

Continuous variables will be presented as mean, standard deviation, median, 25th, and 75th percentile. Categorical variables will be presented as frequency and percentage. Generalized Linear Model (GLM) will be used to assess the effect of intervention on the outcomes of the surveys. The correlation between provider's, parent's, patient's survey will be analyzed using the Spearman's correlation test. All statistical tests will be performed using the R software. All statistical tests will be 2-sided and $p < 0.05$ will be considered as statistically significant.

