1.0 Background and Rationale

Small procedures are an everyday occurrence in the pediatric emergency department. Medical procedures often elicit anxiety, which amplifies the pain response.ⁱ Laceration repair is one of the most common procedures performed. Simple laceration repair can be challenging not from a technical standpoint, but due to patient cooperation secondary to patient pain and anxiety.ⁱⁱ Usually, uncooperative children squirm, kick, twist, and scream; this is physically challenging during a laceration repair. It is the norm for patients to require distraction, analgesia, and anxiolytics as well as physical holding in order to achieve adequate patient stillness for safe repair. Typical passive distraction methods include watching television, playing on a tablet or phone, parental engagement, or Child Life involvement. Distraction is an accessible, low-cost, and non-pharmacologic intervention.

Virtual reality is an evolving technology that allows a viewer to be immersed into a simulated environment using a head mounted device as well as hand-held controllers. Immersive virtual reality is an active form of distraction. Children who actively perform tasks or engage in activities forget about their pain and fear.ⁱⁱⁱ Virtual reality has been documented in the literature as a safe and effective tool to reduce both pain and anxiety surrounding painful procedures in pediatrics as a distraction technique.^{iv} It has also been theorized to diminish pain signals during painful procedures.^v This technology has been studied in burn scrubs,^{vi} wound dressing changes,^{vii} immunizations,^{viii} venipuncture,^{ix} lumbar punctures,^x and dental procedures^{xi} in pediatrics. However, virtual reality (VR) has not been well described for laceration repair in the pediatric emergency department setting. Side effects might include nausea, vomiting, motion sickness, but these have not been proven to be significant outcomes in the literature.^{xii}

In our emergency department, the standard of care involves topical lidocaine/epinephrine/tetracaine (LET) cream and/or subcutaneous lidocaine, positioning, Child Life staff, and distraction. For some children, oral or intranasal anxiolysis is necessary as well as physical holding. Our aim for this study is to determine if Virtual Reality goggles can improve patient pain and anxiety scores during simple laceration repair when compared to standard passive distraction techniques.

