2.0 Objectives

The objective of this study is to determine if VR goggles can decrease patient pain and anxiety during simple laceration repairs. The primary outcome will be pain scores as assessed by the validated Wong Baker Faces Scale and anxiety scores as assessed by the validated Children's Fear Scale. A validated System Usability Scale (SUS) will be measured for each enrolled participant that used the VR goggles. Secondary outcomes include time of procedure, use of physical holding, adverse outcomes, and pharmacologic interventions.

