3.0 Project Procedures

This will be a randomized pragmatic study for all patients ages 6-17 years with simple lacerations. Simple lacerations will be defined as lacerations within the scope of pediatric emergency medicine providers AND not requiring sedation or operative intervention. Subjects will be identified by the Emergency Department staff for enrollment. The goal number of enrolled participants will be 480, including 240 patients randomized into two groups, 120 per group, and 240 parents/guardians. The Emergency Department accepted to participate in this study and ED providers will complete the provider's survey. After signing the consent and assent form when appropriate, the patients will be randomized to either receive the standard of care or standard of care with immersive virtual reality goggles. Consent and assent will be obtained in the patient rooms within the emergency department. The standard of care shall be defined to include any of the following: local analgesia (topical LET and/ or subcutaneous lidocaine), oral or intranasal midazolam, distraction, Child Life Staff, or physical holding. Because each of the aforementioned interventions may vary between patients, it cannot be truly standardized; hence, this will be considered a pragmatic study. Patients randomized to the VR arm will receive the other standard procedures as well with VR goggles as an adjunct. Exclusion criteria include a history of epilepsy, visual or hearing impairment, or intellectual disability that would preclude use of VR goggles as determined by the guardian. Additionally, any lacerations around the eyes, eyebrows, and nose will be excluded as well as patients requiring sedation. Non-English speaking patients will be excluded as well. Hand lacerations will not be excluded.

Participants will be identified by ED staff following evaluation of the laceration. The ED staff will be given a flowchart with eligibility criteria. All interested participants who meet eligibility criteria will be consented. A research team member will obtain consent from parents or guardians by providing and reviewing the consent form (see Subject Consent Form). For patients who are between 8 and 17 years of age, a research team member will obtain assent by providing and reviewing the assent form (see Subject Assent Form). Consent and assent will be obtained in the patient's ED room.

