5.0 Risks to Participants/ HIPAA Privacy Considerations

No personal identifiers will be recorded as part of the research study. Each enrolled participant will be given a unique number for data collection purposes. The risks involved in the study include adverse reactions to the VR goggles, which have been described to rarely cause nausea, vomiting, and motion sickness. There is a theoretical infection risk, but the VR goggles will be cleaned following a decontamination protocol following each use.

The data will be securely stored in RedCAP without any patient identifiers. The paper surveys will be kept in a locked drawer in a locked room within the Pediatric Department of Emergency Medicine offices.

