6.0 Budget

The Virtual Reality goggles are property of the Children's Hospital of the King's Daughters Child Life department. They will be stored in a locked drawer within the CHKD Emergency Department. This project is unfunded.

Figure 1. Use of Immersive Virtual Reality for Laceration Repairs in the Pediatric Emergency
Department
Patient Survey

1. How old are you? _____

2. Have you had stitches before? Yes
 No
 Unsure

3. Have you ever used Virtual Reality (VR) goggles before today? Yes
 No
 Unsure

4. Did you use VR goggles for your stitches today? Yes
 No

5. Would you use VR goggles again to get stitches? Yes
 No

6. During your stitches, did you have any of the following (select all that apply)?
 I did not experience any symptoms
 Dizziness
 Headache
 Nausea
 Vomiting
 Other (describe below)

7. How do you think the stitches went overall? Not well at all
 Somewhat not well
 Neutral
 Somewhat well
 Very well

8. The virtual reality goggles made the stitches seem less scary.
 Strongly disagree
 Disagree
 Neutral
 Agree
 Strongly agree

9. How would you rate your pain:

10. How would you rate how scared you were during the stitches:

[figure not shown]

Figure 2. Use of Immersive Virtual Reality for Laceration Repairs in the Pediatric Emergency
Department
Guardian Survey

1. **Patient Gender:**

Male
 Female
 Non-binary
 Self-identify
 Prefer not to say

2. What is the patient's age? _____

3. Please indicate if the patient has a developmental disability:

A. The patient does not have a developmental disability
B. Autism
C. Cerebral Palsy
D. Intellectual disability
E. Speech delay
F. _____

4. Has the patient had stitches previously? _____

Yes
 No
 Unsure

5. Has the patient ever used Virtual Reality (VR) goggles before today? _____

Yes
 No
 Unsure

6. Did the patient use VR goggles for the procedure today? _____

Yes
 No

7. If, yes, would you use VR goggles again for this procedure? _____

Yes
 No
 Did not use today

8. During the procedure did the patient experience any symptoms (select all that apply)?

Did not experience any symptoms
 Dizziness
 Headache
 Nausea
 Vomiting
 Other (*describe below*)

9. How do you think the procedure went overall?

- Not well at all
- Somewhat not well
- Neutral
- Somewhat well
- Very well

10. In your opinion, did the virtual reality goggles make the procedure seem less scary to the patient?

[figure not shown]
- Strongly disagree
- Disagree
- Neutral
- Agree
- Strongly agree

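### Section 4.0 names a GLM for the symptom items without a test type or sparse-data rule, so a zero cell can give a Wald p near 0.99 or a likelihood-ratio p that is too small

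*Combined protocol and SAP*

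**What the plan says.** Section 4.0 sets the arm comparison in one sentence: "Generalized Linear Model (GLM) will be used to assess the effect of intervention on the outcomes of the surveys". It adds "All statistical tests will be performed using the R software" and "All statistical tests will be 2-sided and $p < 0.05$ will be considered as statistically significant". Categorical variables are to be summarised as counts and percentages. No distribution family, link, covariate list or test type (Wald, likelihood ratio, score) is given. No confidence interval is planned, and no provision is made for outcomes with few or no events.

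Section 2.0 makes the symptoms an endpoint: "Secondary outcomes include time of procedure, use of physical holding, adverse outcomes, and pharmacologic interventions". All three surveys (Figures 1 to 3) carry a symptom checklist that children in both arms can be scored on. The patient version begins "During your stitches, did you have any of the following (select all that apply". The options are dizziness, headache, nausea, vomiting and other.

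On frequency, Section 5.0 says of reactions to the goggles "which have been described to rarely cause nausea, vomiting, and motion sickness". Section 1.0 says "Side effects might include nausea, vomiting, motion sickness, but these have not been proven to be significant outcomes in the literature". Neither section gives a rate, and no control-arm rate appears anywhere. Section 3.0 sets the size: "240 patients randomized into two groups, 120 per group, and 240 parents/guardians".

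**The concern.** A symptom tick box is a yes/no outcome, and the usual GLM for it is logistic regression. Control children wear no headset, so a single symptom such as vomiting could plausibly be absent from that arm. The log odds ratio then has no finite estimate. The fitting routine stops at a large coefficient with an enormous standard error, and the Wald p-value printed by R's standard model summary reflects that breakdown and carries no information about the data. The likelihood-ratio p-value stays finite, but its chi-square approximation is poor at such counts.

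Two readings of the same fit can therefore disagree completely, and the plan does not say which will be used. At stake is the safety comparison for a device used on children. An excess in the VR arm could be reported as no significant difference, or a handful of events could be declared significant. Since the plan's only stated criterion is p < 0.05 and it plans no interval, nothing else would guide the reader on how large a harm remains possible.

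**Working it through.** **Inputs.** From the plan: 120 children per arm (Section 3.0), two-sided 0.05 and R (Section 4.0). Assumed, because the plan gives no symptom rates: control rates of 0.1% to 2% and VR rates of 1% to 8%. The plan states no power or effect size for this outcome, so there is no figure of its own to reproduce beyond 2 × 120 = 240.

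**Step 1: how likely is an empty control cell?** The probability is (1 − r)^120 for true control rate r.

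| Assumed control rate | Chance of no control events |
|---|---|
| 0.1% | 89% |
| 0.5% | 55% |
| 1% | 30% |
| 2% | 9% |

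**Step 2: what each test returns when the control arm has 0 of 120.** A logistic GLM on arm was fitted in R.
- The Wald p comes from the default summary. For 6 against 0 the coefficient is 18.6 with standard error 2669, so z = 0.007 and p = 0.994.
- The likelihood-ratio statistic is 2 Σ O ln(O/E). For 6 against 0 it is 2[6 ln 2 + 114 ln(114/117) + 120 ln(120/117)] = 8.47 on 1 degree of freedom, p = 0.0036.
- Fisher's two-sided p for k against 0 is 2 × C(120,k)/C(240,k). For k = 3 this is 2 × (120 × 119 × 118)/(240 × 239 × 238) = 0.247.

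| VR events, control 0 | Wald | Likelihood ratio | Fisher |
|---|---|---|---|
| 3 | 0.995 | 0.040 | 0.247 |
| 5 | 0.994 | 0.0080 | 0.060 |
| 6 | 0.994 | 0.0036 | 0.029 |
| 10 | 0.991 | 0.0002 | 0.0016 |
| 20 | 0.991 | < 0.0001 | < 0.0001 |

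Wald does not respond to the VR count. Fisher falls below 0.05 from 6 VR events.

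**Step 3: is the likelihood-ratio test a safe substitute?** Exact enumeration over both binomials, with the same true rate in each arm, gives a type I error of 2.5% at 0.5%, 7.3% at 1% and 9.3% at 2%. Fisher stays below 1% at all three rates, which is conservative.

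**Step 4: does the Wald failure persist once the control arm has events?**

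| Control, VR | Wald | Fisher |
|---|---|---|
| 1, 6 | 0.092 | 0.120 |
| 1, 8 | 0.045 | 0.036 |
| 1, 10 | 0.024 | 0.010 |
| 2, 10 | 0.033 | 0.034 |

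It does not.

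**Step 5: power at assumed rates (exact enumeration; a zero cell counts as a Wald non-rejection).**

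| Control, VR rate | Wald | Likelihood ratio | Fisher |
|---|---|---|---|
| 0.5%, 5% | 10% | 73% | 40% |
| 0.5%, 8% | 32% | 94% | 81% |
| 1%, 8% | 45% | 85% | 68% |

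Given at least one control event, Wald and Fisher power are 22% and 20%, 70% and 67%, and 64% and 58% for the same three rows. Wald's whole deficit comes from empty cells. The likelihood-ratio column has to be read with step 3 in mind.

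**Step 6: what an interval would show.** For 6 against 0, the risk difference is 6/120 = 5.0%, with a Newcombe 95% interval of 0.9% to 10.5%. If a symptom never occurs in an arm, the exact two-sided 95% upper limit for its rate there is 1 − 0.025^(1/120) = 3.0%.

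**The case against.** A reader might infer that the GLM breaks down whenever symptoms are few, or that Section 4.0 as written will hide a harm. The documents support neither.

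- **Few is not zero.** The p near 1 needs an empty cell; step 4 shows Wald behaving acceptably with one or two control events.
- **The test is not stated.** A likelihood-ratio test is equally a GLM test and gives 0.0036 for 6 against 0. A Gaussian identity-link GLM gives 0.013. The Wald failure follows from R's default output for a logistic model, which the plan does not name. This stands, but leaving the choice open is itself the gap, because the candidates give opposite answers on the same data.
- **Rare symptoms seldom produce the reversal.** Wald and Fisher disagree about significance, with an empty control cell, only from 6 VR events. At an assumed control rate of 0.5%, the chance of 6 or more VR events with none in control is 0.1%, 1.9% and 8% at VR rates of 1%, 2% and 3%. It reaches 31% and 51% at 5% and 8%. The higher rates are assumptions.
- **The control cell may not be empty.** The description as rare covers nausea, vomiting and motion sickness from the goggles. The checklists also list dizziness, headache and other, and Section 3.0 allows midazolam and subcutaneous lidocaine in either arm. An any-symptom outcome is less likely to be empty than a single item.
- **Counts will be shown.** Planned frequencies and percentages would put 6 and 0 beside the p-value. That softens the risk but supplies no interval.

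Nor do the documents support extending the point to every yes/no outcome. At 9 against 25 events, Wald gives 0.0044 and Fisher 0.0049, so the GLM is adequate there.

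**Conclusion.** The point holds in a limited form. Section 4.0 does not specify the GLM's test type and has no method for sparse symptom data. If the control arm has no events for a symptom, the default logistic Wald p is about 0.99 regardless of the VR count, while the likelihood-ratio p is too small at very low counts. At 3 against 0 the two readings of one model are 0.995 and 0.040, with Fisher at 0.247.

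How often this would matter rests on assumed rates. The empty-cell chances of 55% and 30% assume control rates of 0.5% and 1%, and the power losses assume VR rates of 5% to 8%. The arithmetic for a given table does not depend on those assumptions. The point concerns a secondary safety outcome and leaves the primary pain and fear comparisons untouched. The correction is worth making because it is right whichever GLM test was intended.

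**What to change.** In Section 4.0, for the adverse-symptom items only, replace the GLM p-value with three things: n/N by arm, the risk difference with a Newcombe or Miettinen-Nurminen 95% confidence interval, and a two-sided Fisher exact p-value. State that the safety conclusion rests on the confidence interval and that p ≥ 0.05 will not be read as evidence of safety. Say also which rater's report and which symptom definition (each symptom, any symptom, or both) the table uses, since three surveys collect the item.

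Keep physical holding, anxiolytic use and other non-sparse yes/no outcomes in the GLM, state its family, link and test, and specify a Firth penalized fit if an arm has zero events.

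The cost is a few sentences and no new data. The symptom items lose covariate adjustment, and Fisher's test is somewhat conservative, which is a further reason to lead with the interval.

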5.0 Risks to Participants/ HIPAA Privacy Considerations

No personal identifiers will be recorded as part of the research study. Each enrolled participant will be given a unique number for data collection purposes. The risks involved in the study include adverse reactions to the VR goggles, which have been described to rarely cause nausea, vomiting, and motion sickness. There is a theoretical infection risk, but the VR goggles will be cleaned following a decontamination protocol following each use.

The data will be securely stored in RedCAP without any patient identifiers. The paper surveys will be kept in a locked drawer in a locked room within the Pediatric Department of Emergency Medicine offices.

6.0 Budget

The Virtual Reality goggles are property of the Children's Hospital of the King's Daughters Child Life department. They will be stored in a locked drawer within the CHKD Emergency Department. This project is unfunded.

Figure 1. Use of Immersive Virtual Reality for Laceration Repairs in the Pediatric Emergency
Department
Patient Survey

1. How old are you? _____

2. Have you had stitches before? Yes
 No
 Unsure

3. Have you ever used Virtual Reality (VR) goggles before today? Yes
 No
 Unsure

4. Did you use VR goggles for your stitches today? Yes
 No

5. Would you use VR goggles again to get stitches? Yes
 No

6. During your stitches, did you have any of the following (select all that apply)?
 I did not experience any symptoms
 Dizziness
 Headache
 Nausea
 Vomiting
 Other (describe below)

7. How do you think the stitches went overall? Not well at all
 Somewhat not well
 Neutral
 Somewhat well
 Very well

8. The virtual reality goggles made the stitches seem less scary.
 Strongly disagree
 Disagree
 Neutral
 Agree
 Strongly agree

9. How would you rate your pain:

10. How would you rate how scared you were during the stitches:

[figure not shown]

Figure 2. Use of Immersive Virtual Reality for Laceration Repairs in the Pediatric Emergency
Department
Guardian Survey

1. **Patient Gender:**

Male
 Female
 Non-binary
 Self-identify
 Prefer not to say

2. What is the patient's age? _____

3. Please indicate if the patient has a developmental disability:

A. The patient does not have a developmental disability
B. Autism
C. Cerebral Palsy
D. Intellectual disability
E. Speech delay
F. _____

4. Has the patient had stitches previously? _____

Yes
 No
 Unsure

5. Has the patient ever used Virtual Reality (VR) goggles before today? _____

Yes
 No
 Unsure

6. Did the patient use VR goggles for the procedure today? _____

Yes
 No

7. If, yes, would you use VR goggles again for this procedure? _____

Yes
 No
 Did not use today

8. During the procedure did the patient experience any symptoms (select all that apply)?

Did not experience any symptoms
 Dizziness
 Headache
 Nausea
 Vomiting
 Other (*describe below*)

9. How do you think the procedure went overall?

- Not well at all
- Somewhat not well
- Neutral
- Somewhat well
- Very well

10. In your opinion, did the virtual reality goggles make the procedure seem less scary to the patient?

[figure not shown]
- Strongly disagree
- Disagree
- Neutral
- Agree
- Strongly agree

11. How would you rate the patient's pain:

Wong-Baker FACES® Pain Rating Scale

12. How would you rate the patient's fear:

No fear A little fear Some fear A lot of fear The most fear

Figure 3. Use of Immersive Virtual Reality for Laceration Repairs in the Pediatric Emergency
Department
Provider Survey

1. Procedure Duration (*from irrigation to closure end*):
A. <10 minutes
B. 10-15 minutes
C. 16-20 minutes
D. 21-25 minutes
E. >25 minutes

2. Did the patient use VR goggles for the procedure today?
 Yes
 No

3. Would you recommend VR goggles again for this procedure?
 Yes
 No

4. Did the patient need to be held during the procedure?
 Yes
 No

5. Did the patient receive medicine intended to help them stay calm?
 Yes
 No

6. During the procedure, did the patient experience any symptoms (select all that apply)?
 Did not experience any symptoms
 Dizziness
 Headache
 Nausea
 Vomiting
 Other (*describe below*)

7. How do you think the procedure went overall?
 Not well at all
 Somewhat not well
 Neutral
 Somewhat well
 Very well

8. In your opinion, did the virtual reality goggles make the procedure seem less scary to the patient?

Strongly disagree
 Disagree
 Neutral
 Agree
 Strongly agree

9. How would you rate the patient's pain:

10. How would you rate the patient's fear:

[figure not shown]

Figure 4. Education Plan for Disinfection Protocol for Virtual Reality Goggles

1. The company insert for cleansing the virtual reality goggles will be printed, laminated, and physically located with the goggles in their carrying case.
2. The protocol for cleaning will be addressed during an Emergency Medicine division meeting prior to the start of the project and detailed in the meeting minutes.
3. The protocol will be addressed during a pediatrics monthly resident meeting and dispersed in an email from the chief residents.
4. The protocol will be emailed to all rotating residents prior to the start of their rotation.
5. The protocol will also be disseminated to nursing staff and ED techs via [name] prior to the start of the project.
6. Research project staff will be available either in person or by phone to answer any questions regarding the disinfection protocol during the study phase of the project. Contact information will be included inside the carrying case for the goggles as well as on all written communications (division meeting minutes, chief email, etc.)

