Patients will be separated into groups age 6-11 and 12-17. Patients will be randomized via a selection of a sealed envelope which will contain instructions for use of the VR goggles. The goggles utilized will be Lenovo Mirage Solo with DayDream, which are standalone VR headset with WorldSense Body Tracking. Research staff will coach the child on age-appropriate games, as previously determined by Lenovo.

The goggles will be cleansed with Oxivir Tb disinfectant wipes after each use and allowed to dry in room air prior to next use. Education will be provided to all ED providers on the proper cleansing protocol for the VR goggles (Figure 4). The disinfectant protocol will be available for all users during the study, and has been approved by the director of Infection Control at Children's Hospital of the King's Daughters.

Following the laceration repair, the patient, guardian and health care provider will be surveyed (Figure 1, 2, and 3) on paper surveys. The survey includes Likert-type scale questions, binary

questions as well as incorporates the Wong Baker Faces Pain Scale and Children's Fear Scale. The duration of the procedure will be recorded by the healthcare provider who completed the laceration repair. Time of procedure will be defined as from the time of irrigation to wound dressing. Patients and parents will both be filling out their own individual surveys. The parent should complete the survey first before the child should the child need assistance with completion. Patients and parents may decline to participate in any survey at any time.

The recruitment period will be from November 2021 until February 2021. Enrolled participants will not be compensated, and enrollment will be completely voluntary.

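### The symptom item on all three forms covers only the repair itself, so headset symptoms that begin outside it are not explicitly asked for

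*Combined protocol and SAP*

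**What the plan says.** Section 2.0 (Objectives) makes adverse outcomes an endpoint: "Secondary outcomes include time of procedure, use of physical holding, adverse outcomes, and pharmacologic interventions". Section 5.0 gives the anticipated harms of the device as "adverse reactions to the VR goggles, which have been described to rarely cause nausea, vomiting, and motion sickness", without a rate or an onset time.

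The only collection described is one tick-box item per survey, completed after the repair:

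- Figure 1 (Patient Survey), item 6: "During your stitches, did you have any of the following (select all that apply"
- Figure 2 (Guardian Survey), item 8: "During the procedure did the patient experience any symptoms (select all that apply"
- Figure 3 (Provider Survey), item 6: "During the procedure, did the patient experience any symptoms (select all that apply"

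The response options, including the free-text one, sit under the same time-limited question on each form. Section 3.0 says of the headset that "Research staff will coach the child on age-appropriate games". It does not say when this happens relative to irrigation, whether the headset is worn at the time, or when the headset is put on and taken off. For the duration outcome it states: "Time of procedure will be defined as from the time of irrigation to wound dressing". The provider form's duration item stops at the end of closure instead. No adverse-event log, headset-specific symptom check or later contact is described.

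**The concern.** The exposure of interest for harm is time in the headset, but the question is tied to the time of suturing. The two need not coincide. Symptoms may begin, or be noticed, after the repair has ended or the headset has been removed. If the coaching involves wearing the headset before irrigation, they may also begin then. A child who vomits after the dressing is on, but before the form is filled in, can truthfully tick that there were no symptoms during the stitches.

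At stake is the secondary safety comparison. Section 5.0 describes these reactions as rare, so few are expected among 120 VR patients, and losing some of them could leave a reassuring count of none or nearly none. The primary pain and fear scores are not affected.

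**Working it through.** **Step 1. Is there another route by which symptoms are captured?** Comparing Sections 2.0, 3.0, 4.0 and 5.0 with Figures 1 to 3 shows none. All three informants are asked about the same limited period, so having three of them does not widen it.

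**Step 2. What falls outside the window as worded?**

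| Onset of symptom | Inside the wording? |
|---|---|
| During the repair | Yes |
| After the repair, before the form is completed | No, on a literal reading |
| After headset removal | No, if removal is at or after the end of the repair; removal time is not stated |
| During coaching | No, if coaching precedes irrigation; timing and headset wear are not stated |
| After the form is completed | No; no later contact is described |

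**Step 3. Direction.** A symptom caused by the headset can occur only in a child who wore it. Losing such symptoms lowers the count among headset users and cannot lower it among children who never wore one. Symptoms from other causes, such as medicines available to both arms, can be lost in either arm.

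**Step 4. Illustration of size.** The plan states no symptom rate, power or margin for adverse outcomes, so there is no figure of its own to reproduce.

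- From the documents: n = 120 patients in the VR arm (Section 3.0).
- Assumed: true VR symptom risk p of 2% or 5%; share f of onsets outside the window of 10%, 25% or 50%; no out-of-window symptom is reported.
- Recorded risk q = p × (1 − f). Expected recorded events = 120 × q. Chance of recording none = (1 − q)^120.

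| p | f | q | Expected events | Chance of none |
|---|---|---|---|---|
| 2% | 0 | 2.0% | 2.4 | 0.98^120 = 8.9% |
| 2% | 10% | 1.8% | 2.16 | 0.982^120 = about 11% |
| 2% | 25% | 1.5% | 1.8 | 0.985^120 = about 16% |
| 2% | 50% | 1.0% | 1.2 | 0.99^120 = about 30% |
| 5% | 0 | 5.0% | 6.0 | 0.95^120 = 0.2% |
| 5% | 10% | 4.5% | 5.4 | 0.955^120 = about 0.4% |
| 5% | 25% | 3.75% | 4.5 | 0.9625^120 = about 1.0% |
| 5% | 50% | 2.5% | 3.0 | 0.975^120 = 4.8% |

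A misleading zero is a practical possibility mainly at the lower risk. At 5%, the chance of a zero stays below 5% even if half of the onsets are missed, and the effect is a lower count.

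**The case against.** Four arguments on the other side carry weight.

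1. **Coaching.** A reader might infer that children wear the headset before the repair and that symptoms at that stage are lost. Section 3.0 does not say when coaching occurs or whether the headset is on, so this part can only be conditional. The part about onset after the repair does not depend on it.

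2. **Loose reading of the question.** A reader might infer that out-of-window symptoms will go unrecorded. The irrigation-to-dressing definition belongs to the duration outcome and is not printed on the patient or guardian form. The patient form also uses the word stitches for the whole episode, for instance when asking how they went overall. A guardian whose child has just vomited may well tick the box. The supportable statement is that such symptoms are not explicitly asked for. Capture then depends on how each respondent reads the item, which is still a measurement weakness.

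3. **Net bias.** A reader might infer a known bias in the between-arm difference. Under-counting of headset-caused symptoms is the likely direction. But symptoms from other causes may also be missed in both arms, and the net effect cannot be computed without rates and onset times that the plan does not give.

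4. **Importance.** This is one item behind a secondary outcome, and the plan announces no formal safety conclusion. That limits the weight of the point. It does not remove it, because adverse outcomes are a named endpoint and nothing else in the plan would capture them.

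**Conclusion.** The concern holds in limited form. All three symptom items are restricted to the repair, they are the only adverse-outcome capture described, and symptoms beginning after the repair or after headset removal are not explicitly asked for. Whether coaching adds to the gap is unknown from the documents.

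The likely direction is under-counting of VR harm. Its size cannot be derived from the plan: the table above rests on assumed risks, assumed out-of-window shares and complete non-reporting outside the window, so for each assumed risk and share it shows the largest loss. The documents do not support the stronger conclusion that the trial's safety result will be falsely reassuring. The change is worth making before enrolment because, with no later contact described, what is not asked at the survey is unlikely to be recovered.

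**What to change.** In both arms, reword the patient and guardian items in plain language to run from group assignment, before any headset use, until the form is completed. For example: *From when you were told whether you would use the VR goggles until now, did you feel any of these?* Add a tick for onset before, during or after the repair. Assignment gives both arms the same starting point, and a child can understand the wording.

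Give the provider item the same window, limited to what the provider observed or was told, since the provider may not have been present throughout.

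In Section 4.0, state that adverse outcomes are analysed on this window and that the during-repair subset is reported separately.

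The cost is one reworded item and one added tick on three paper forms, a few more seconds per form, and a slightly higher recorded symptom rate in both arms. Symptoms that begin after the survey would still not be captured, so any safety statement should be limited to the period up to survey completion.
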